9.9 Health Economics OR Medical Resource Utilization and Health Economics .	27
10. STATISTICAL CONSIDERATIONS	28
10.1 Sample Size Determination.....	28
10.2 Populations for Analyses	28
10.3 Statistical Analyses	28
10.3.1 Efficacy Analyses	28
10.3.2 Safety Analyses	28
10.3.3 Pharmacokinetic Analyses	28
11. REFERENCES	29
12 APPENDICES	32
APPENDIX 1 ABBREVIATIONS AND TRADEMARKS	33
APPENDIX 2 STUDY GOVERNANCE CONSIDERATIONS	39
APPENDIX 3 ADVERSE EVENTS AND SERIOUS ADVERSE EVENTS: DEFINITIONS AND PROCEDURES FOR RECORDING, EVALUATING, FOLLOW UP AND REPORTING.....	48
APPENDIX 4 WOMEN OF CHILDBEARING POTENTIAL DEFINITIONS AND METHODS OF CONTRACEPTION.....	52
APPENDIX 5 DIAGNOSTIC CRITERIA FOR DRUG AND ALCOHOL ABUSE..	56

1 **SYNOPSIS**

Protocol Title: A Clinical Study to Evaluate the Steady State Pharmacokinetics of Baraclude in Participants with Hepatitis B Virus Infection

Study Phase: IV (post-marketing)

Rationale:

While pharmacokinetics of Baraclude® has been investigated in the global HBV clinical trial population, pharmacokinetic (PK) information specifically for Japanese patients diagnosed with HBV infection has not been studied. Such pharmacokinetic information may provide a better understanding of Baraclude in a real-world clinical setting in Japan.

Study Population:

Inclusion Criteria

- a) Participants with chronic hepatitis B (CHB) (excluding participants with a superinfection) who have been confirmed to have CHB by one of the following:
 - i) Detectable Hepatitis B surface antigen (HBsAg) at screening and for at least 24 weeks prior to screening or detectable HBsAg for < 24 weeks and negative for IgM core antibody and confirmation of chronic hepatitis on liver biopsy
 - ii) Documentation of positive Hepatitis e antigen (HBeAg) status at screening and at least once \geq 4 weeks prior to screening
- b) Participants whose condition is stable in the investigator's judgement
- c) Participants who are being treated with 0.5 mg daily of Baraclude for a minimum of 10 consecutive days prior to the study enrollment
- d) Creatinine clearance is > 50 mL/min

Exclusion Criteria

- a) Lamivudine-refractory participants
- b) Any significant, acute illness or chronic medical illness that is not stable and/or untreated
- c) Current or recent (within 3 months of Baraclude administration) gastrointestinal disease that could impact upon the absorption of study drug
- d) Any gastrointestinal surgery that could impact upon the absorption of study drug
- e) Inability to be venipunctured and/or tolerate venous access

Objectives and Endpoints:

Objective	Endpoint
Primary	

Objective	Endpoint

to evaluate the steady state of Baraclude pharmacokinetics in HBV-infected participants	
pharmacokinetic parameter values derived from plasma concentration versus time data using non-compartmental methods
Secondary	

Not applicable	
Not applicable.

Overall Design:

This is an open label, single-dose, steady state pharmacokinetics (PK) study of Baraclude in Japanese HBV-infected participants. Participants will undergo a screening evaluation to determine eligibility within 21 days prior to administration of study drug. Participants will be admitted into the clinical site prior to study drug administration. On this day (Day 1), Baraclude will be administered, and breakfast will be provided 2 hours after administration.

Participants will remain at the clinical site for approximately 2 days following administration of the single dose of study medication. The initial time of dose administration will be called “0” hour. At the time of dosing, 240 mL of water will be administered to the participants with the dose.

PK samples will be taken as described in the Schedule of Activities.

The study design schematic is presented in Table below.

Study Schematic

Day -21 or Later	Day 1	Day 2
Screening and Enrollment	Treatment with Baraclude	PK Assessment
Laboratory assessments	PK Assessments	Study discharge

Physical examinations, vital sign measurements, and clinical laboratory evaluations will be performed at screening. Blood samples will be collected for up to 24 hours after study drug administration for pharmacokinetic (PK) analysis. Participants will be closely monitored for adverse events throughout the study.

Number of Participants:

Approximately 8 participants will be enrolled.

Treatment Arms and Duration:

Participants will take 1 dose of 0.5 mg Baraclude in the clinic facility on Day 1. The local marketed Baraclude will be used as study treatment in this study. Approximately 2 days after Baraclude administration, participants will leave the clinical site if they have not experienced any adverse events or are in a condition to be released according to the investigator's clinical judgement. The approximate duration of this study is 2 days plus up to 3 weeks for the screening period.

Study treatment:

Study Drug for AI463528		
Medication	Potency	IP/Non-IP
Baraclude	0.5 mg	IP

2. SCHEDULE OF ACTIVITIES

Table 2-1: Screening Procedural Outline (AI463528)

Procedure	Screening Day -21 Visit	Notes
Eligibility Assessments		
Informed Consent	X	A participant is considered enrolled only when a protocol-specific informed consent is signed.
Inclusion/Exclusion Criteria	X	
Medical History	X	Include any toxicities or allergy related to previous treatments.
Safety Assessments		
Physical Examination (PE)	X	If the screening PE is performed within 24 hours prior to dosing on Day 1, then a single exam may count as both the screening and pre-dose evaluation.
Physical Measurements	X	Includes height, weight, and BMI.
Vital Signs	X	Includes body temperature, respiratory rate, seated blood pressure, and heart rate. Blood pressure and heart rate should be measured after the participant has been resting quietly for at least 5 minutes. Consider alternate position(s) for vital sign collection.
Concomitant Medication Use	X	
Electrocardiogram (ECGs)	X	ECGs should be recorded after the participant has been supine for at least 5 minutes.
Laboratory Tests		
Serology	X	Includes hepatitis C antibody, HIV-1 and -2 antibody, and CrCl.
Pregnancy Test	X	For WOCBP only. Urine or serum.
Serum creatinine	X	
Adverse Event Reporting		
Monitor for Serious Adverse Events		All SAEs must be collected from the date of participant's written consent until 30 days after discontinuation of dosing or participant's participation in the study if the last scheduled visit occurs at a later time

Table 2-2: On Treatment Procedural Outline(AI463528)

Procedure	Day 1	Study Discharge	Notes
Safety Assessments			
Physical Examination (PE)	X		
Physical Measurements	X		Weight only
Vital Signs	X		Includes body temperature, respiratory rate, and seated blood pressure, and heart rate. Blood pressure and heart rate should be measured after the participant has been resting quietly for at least 5 minutes. Consider alternate position(s) for vital sign collection.
Concomitant Medication Use	X		
Adverse Event Reporting			
Monitor for Adverse Events and Serious Adverse Events	X	X	See note in screening procedures.
Pharmacokinetic (PK) Assessments			
Serial Blood PK Sampling	X	X	See Section 9.5 .
Clinical Drug Supplies			
Study Drug Administration	X		Supplied by the participant.

Abbreviations: D=Day

3. INTRODUCTION

Chronic infection with Hepatitis B Virus (HBV) is a cause of substantial morbidity and mortality, around the world. Approximately 350 to 400 million people worldwide have chronic hepatitis B (CHB) infection,^{1,2} and over 1 million people die each year from complications of cirrhosis and primary hepatocellular carcinoma (HCC).³

HBV genomic sequences have been classified into at least eight genotypes (A through H) based on a divergence of 8% or more over the complete nucleotide sequence.^{4,5} These genotypes vary worldwide and have distinct geographic distributions.^{6,7,8} Japanese patients with chronic HBV infection often have genotypes B and C⁹ whereas those with acute infection are more likely to have genotype A.^{10,11} In addition, studies suggest that acute infection with HBV genotype A may be associated with an increased risk of progression to persistent infection.¹²

Chronic intrahepatic replication of HBV also appears to be a critical event in the pathogenesis of liver injury, and results in an ongoing cascade of inflammation, injury, and repair. This recurring inflammatory cycle leads to scarring (fibrosis), progression to cirrhosis, and to dysregulation of hepatocyte regeneration with the potential for HCC.

Intrahepatic replication of the virus appears to be a critical factor in HBV disease progression. A meta-analysis of epidemiology studies concluded that the risk for HCC increased 20-fold for individuals who were hepatitis B surface antigen (HBsAg)-positive compared with those who were HBsAg-negative.¹³ Another study found that, compared to HBsAg-negative controls, the relative risk for HCC was 9.6 in HBsAg-positive patients and 60.2 in those who were also HBeAg-positive.¹⁴ These data suggest that optimal anti-HBV therapy would provide sustained inhibition of viral replication, leading to improved clinical outcomes. A direct link between antiviral therapy and clinical outcome was established in a 32-month study in which continuous treatment with lamivudine (LVD) approximately halved the rate of hepatic decompensation and reduced the risk of HCC among patients with CHB infection and advanced fibrosis or cirrhosis at baseline.¹⁵

Approved therapies for CHB infection include interferon alfa, peginterferon alfa-2a,¹⁶ LVD,¹⁷ adefovir dipivoxil (ADV),¹⁸ Baraclude® (entecavir), telbivudine (LdT), and tenofovir disoproxyl fumarate (TDF).¹⁹ The recombinant alfa interferons act primarily as endogenous immunomodulatory agents and also have intrinsic antiviral effects. Interferon is administered by injection and is frequently associated with fever, flu-like symptoms, neutropenia, and depression. Lamivudine, ADV, LdT, TDF, and Baraclude are nucleoside analogs (NAs) that directly inhibit viral replication. Lamivudine is well tolerated, but efficacy is limited by resistance, which develops at a rate of 15% to 25% during the first year of treatment and up to 70% after 4 years of treatment.²⁰ The emergence of lamivudine-resistant (LVDr) virus is usually associated with renewed HBV replication and a subsequent reduction in clinical efficacy.²¹ Among subjects with pre-existing LVDr, rates of ADV resistance (ADVr) are reported to be 18% after 1 year and 25% after 2 years

of therapy.^{22,23} Adefovir therapy is associated with a potential risk of nephrotoxicity.¹⁸ The efficacy of LdT was demonstrated in Phase 3 controlled study of nucleoside-naïve subjects with HBeAg-positive or HBeAg-negative HBV infection. Genotypic analysis detected amino acid substitutions associated with virologic failure in 49 of 103 HBeAg-positive subjects and 12 of 12 HBeAg-negative subjects after \geq 16 weeks of treatment.¹⁹ Tenofovir is approved for the treatment of CHB based on the results of 2 Phase 3 controlled studies in HBeAg-positive and HBeAg-negative subjects.²⁴

Overall, based on the efficacy and safety results of Phase 2/3 studies of Baraclude vs LVD, a Phase 3b study of Baraclude vs ADV in CHB patients with compensated liver disease, and a Phase 3b study of Baraclude vs ADV in patients with decompensated liver disease, as well as pediatric studies, Baraclude is an important treatment option among available oral HBV therapies

3.1 Study Rationale

While pharmacokinetics of Baraclude has been investigated in the global HBV clinical trial population, pharmacokinetic (PK) information specifically for Japanese patients diagnosed with HBV infection has not been studied. Such pharmacokinetic information may provide a better understanding of Baraclude in a real world clinical setting in Japan.

3.2 Background

3.2.1 Pharmacology

For physical/chemical and pharmaceutical properties and formulation, refer to the Investigator Brochure Section 3.²⁵

3.2.2 Toxicity

Dose-related systemic exposures to Baraclude were established after multiple doses in nonclinical toxicology species. Mean steady-state exposures in toxicology studies \geq 3 months in duration were up to 2,500 times greater than the mean steady-state exposure in humans at 1.0 mg.

3.2.3 Preclinical Metabolism and Pharmacokinetics

Mechanism of Action

Baraclude is efficiently phosphorylated to entecavir (ETV)-TP by cellular nucleoside kinases. By competing directly with the natural substrate, dGTP, ETV-TP functionally inhibits all 3 activities of the viral polymerase: (1) priming of the HBV polymerase; (2) reverse transcription negative strand DNA synthesis; and (3) DNA polymerase activity responsible for positive strand DNA synthesis.

Entecavir-triphosphate has $>$ 15-fold and $>$ 30-fold potency than the active phosphorylated forms of LVD and ADV, respectively, in inhibiting polymerization.²⁶

In Vitro Antiviral Activity

Baraclude inhibited HBV DNA synthesis (EC50) at a concentration of 0.004 μ M in human HepG2 cells transfected with wild-type HBV. The median EC50 value for Baraclude against LVDr HBV (rtM204V, rtL180M) was 0.026 μ M (range 0.010-0.059 μ M). ^{27,28,29,30}

3.2.4 Pharmacokinetics of Baraclude

In healthy subjects, Baraclude was rapidly absorbed, with peak plasma concentrations occurring between 0.5 and 1.5 hours. There was a dose-proportionate increase in peak plasma concentration (Cmax) and area under concentration-time curve (AUC) values following multiple doses ranging from 0.1 to 1 mg. Steady-state was achieved after 6-10 days of once daily (QD) dosing with approximately 2-fold accumulation. Maximum observed concentration and trough plasma concentration at steady state were 4.2 and 0.3 ng/mL, respectively, for a 0.5-mg dose, and 8.2 and 0.5 ng/mL, respectively, for a 1 mg dose. In healthy subjects, the bioavailability of the tablet was 100% relative to the oral solution. The oral solution and tablet may be used interchangeably. ^{31,32,33}

Oral administration of Baraclude 0.5 mg with a standard high-fat meal (945 kcal, 54.6 g fat) or a light meal (379 kcal, 8.2 g fat) resulted in a minimal delay in absorption (1-1.5 hour fed vs 0.75 hour fasted), a decrease in Cmax of 44% to 46%, and a decrease in AUC of 18% to 20%. ^{34,35}

The estimated volume of distribution for Baraclude was in excess of total body water, suggesting that it has good penetration into tissues. Protein binding to human serum protein in vitro was approximately 13%. ^{31,33,36}

Baraclude is not a substrate, inhibitor, or inducer of the cytochrome P-450 (CYP450) enzyme system. Following administration of 14C-ETV in humans and rats, no oxidative or acetylated metabolites and minor amounts of Phase 2 metabolites (glucuronide and sulfate conjugates) were observed. ^{33,37,38,39,40} After reaching peak levels, Baraclude plasma concentrations decreased in a bi-exponential manner with a terminal elimination half-life of approximately 128-149 hours. The observed drug accumulation index is approximately 2-fold with daily dosing, suggesting an effective accumulation half-life of about 24 hours. ^{31,33}

Baraclude is predominantly eliminated by the kidney, with urinary recovery of unchanged drug at steady-state ranging from 62% to 73% of the dose. Renal clearance is independent of dose and ranges between 360 and 471 mL/min suggesting that Baraclude undergoes both glomerular filtration and net tubular secretion. ^{31,33}

3.3 Benefit/Risk Assessment

Baraclude has been approved for the treatment of HBV in Japan since 2006. Participants in this study routinely take Baraclude as part of their daily medication for the management of HBV; therefore, there is no additional risk. In this study, participants will experience 12 venipunctures for blood draws for screening assessments and PK assessments. There is a small risk of infection with each venipuncture. The data collected from this study will add to the understanding of real-world use of Baraclude in HBV Participants in Japan.

4. OBJECTIVES AND ENDPOINTS

Table 4-1: Objectives and Endpoints

Objectives	Endpoints
Primary	
 to evaluate the steady state of Baraclude pharmacokinetics in HBV-infected participants
Secondary	
 Not applicable.
Tertiary/Exploratory	
 Not applicable

5. STUDY DESIGN

5.1 Overall Design

This is an open-label, single-dose, steady state pharmacokinetics (PK) study of Baraclude in Japanese HBV participants. Participants will undergo a screening evaluation to determine eligibility within 21 days prior to administration of study drug. Participants will be admitted into the clinical site prior to study drug administration. On this day (Day 1), Baraclude will be administered, and breakfast will be provided 2 hours after administration.

Participants will remain at the clinical site for approximately 2 days following administration of the single dose of study medication. The initial time of dose administration will be called “0” hour. At the time of dosing, 240 mL of water will be administered to the participants with the dose.

Participants will take 1 dose of 0.5 mg Baraclude in the clinic facility on Day 1. The local marketed Baraclude will be used as study treatment in this study. PK samples will be taken as described in [Table 9.5-1](#). Approximately 2 days after Baraclude administration, participants will leave the clinical site if they have not experienced any adverse events or are in a condition to be released according to the investigator’s clinical judgement. The approximate duration of this study is 2 days and up to 3 weeks for the screening period.

Participants are asked to take Baraclude once daily at the same time in the day (eg, 9:00AM) for 10 days before entering the clinical site.

The study design schematic is presented in Table 5.1-1.

Table 5.1-1: Study Schematic

Day -21 or Later	Day 1	Day 2
Screening and Enrollment	Treatment with Baraclude	PK Assessment
Laboratory assessments	PK Assessments	Study discharge

Physical examinations, vital sign measurements, and clinical laboratory evaluations will be performed at screening. Blood samples will be collected for up to 24 hours after study drug administration for pharmacokinetic (PK) analysis. Approximately 30 mL of blood will be drawn from each participant for screening assessments (8 mL) and PK assessments (22 mL) during the study. Participants will be closely monitored for adverse events throughout the study.

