7.1 Treatments Administered

The selection and timing of dose for each participant is as follows:

Table 7.1-1: Selection and Timing of Dose

Study Treatment	Unit dose strength(s)/Dosage level(s)	Dosage formulation Frequency of Administration	Route of Administration
Baraclude	0.5 mg	1 dose at 9:00 am of Day 1 (\pm 30 minutes)	oral

The local marketed Baraclude will be used as study treatment in this study.

Restrictions related to food and fluid intake are described in [Section 6.3](#).

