7.4 Dosage Modification

Participants will receive a single dose of Baraclude 0.5 mg. No dose modifications are permitted during the conduct of the study or for 10 days prior to Day 1.

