Planned time points for all safety assessments are listed in the Schedule of Activities.

9.4.1 *Clinical Safety Laboratory Assessments*

- Investigators must document their review of each laboratory safety report. Investigators must confirm the laboratory test results for participant's eligibility.

Results of clinical laboratory tests performed as part of screening must be available prior to dosing.

9.4.2 *Imaging Safety Assessment*

Not applicable.

9.5 *Pharmacokinetics*

Pharmacokinetics of Baraclude will be derived from plasma concentration versus time. The pharmacokinetic parameters to be assessed include:

Cmax	Maximum observed plasma concentration
Tmax	Time of maximum observed plasma concentration
Ctrough	Trough observed plasma (predose) concentration
C24	Observed plasma concentration at 24 hours postdose
AUC(TAU)	Area under the concentration-time curve in one dosing interval
CLT/F	Apparent total body clearance

[Table 9.5-1](#) lists the sampling schedule to be followed for the assessment of pharmacokinetics. Further details of blood collection and processing will be provided to the site in the procedure manual.

Individual participant pharmacokinetic parameter values will be derived by non-compartmental methods by a validated pharmacokinetic analysis program. Actual times will be used for the analyses.

Table 9.5-1: Pharmacokinetic Sampling Schedule for AI463528

Study Day of Sample Collection	Event	Time (Relative To Baraclude Dose) Hour: Min
1	predose	00:00
1	0.25	00:15
1	0.5	00:30
1	1.0	01:00
1	1.5	01:30
1	2	02:00
1	4	4:00
1	6	6:00
1	8	8:00
1	12	12:00
2	24	24:00

The plasma will be analyzed for Baraclude by a validated assay.

In addition, plasma samples will be archived for potential metabolite analysis, if the need arises and to the extent possible.

Detailed instructions for the pharmacokinetic plasma collection, labeling, processing, storage, and shipping will be provided to the site in the procedure manual.

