2. STUDY DESCRIPTION

2.1 Study Design

This is an open-label, single-dose, steady state pharmacokinetics (PK) study of Baraclude in Japanese HBV participants. Participants will undergo a screening evaluation to determine eligibility within 21 days prior to administration of study drug. Eligible participants include those that are taking 0.5 mg daily Baraclude for a minimum of 10 consecutive days prior to study enrollment.

Participants will be admitted into the clinical site prior to study drug administration. On this day (Day 1), Baraclude will be administered, and breakfast will be provided 2 hours after administration.

Participants will remain at the clinical site for approximately 2 days following administration of the single dose of study medication. The initial time of dose administration will be called “0” hour. At the time of dosing, 240 mL of water will be administered to the participants with the dose.

Participants will take 1 dose of 0.5 mg Baraclude in the clinic facility on Day 1. The local marketed Baraclude will be used as study treatment in this study. PK samples will be taken as described in **Table 4.3-2**. Approximately 2 days after Baraclude administration, participants will leave the clinical site if they have not experienced any adverse events or are in a condition to be released according to the investigator’s clinical judgement. The approximate duration of this study is 2 days as well as up to 3 weeks for the screening period.

Participants are asked to take Baraclude once daily at the same time in the day (e.g., 9:00AM) for 10 days during screening before entering the clinical site.

The study design schematic is presented in Table 2.1-1.

Table 2.1-1: Study Schematic

Day -21 or Later	Day 1	Day 2
Screening and Enrollment Laboratory assessments	Treatment with Baraclude PK Assessments	PK Assessment Study discharge

Physical examinations, vital sign measurements, and clinical laboratory evaluations will be performed at screening. Blood samples will be collected for up to 24 hours after study drug administration for PK analysis. Participants will be closely monitored for adverse events throughout the study.

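### Minor: home doses before Day 1 are not tied to the fixed 9:00 am Day 1 dose, so a compliant evening taker is sampled about 12 h after the last dose and C0, C24 and AUC(TAU) come out slightly high

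*Protocol*

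**What the plan says.** **Home dosing.** Protocol 5.1: "Participants are asked to take Baraclude once daily at the same time in the day (eg, 9:00AM) for 10 days". The period is stated as "for 10 days before entering the clinical site"; SAP 2.1 words it as "for 10 days during screening before entering the clinical site" and also gives 9:00 am only as an example. The entry criterion in Protocol 6.1 (0.5 mg daily for at least 10 consecutive days) names no clock time.

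**Day 1 dose.** Protocol Table 7.1-1: "1 dose at 9:00 am of Day 1", with a tolerance of 30 minutes either way.

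**Admission.** Protocol 5.1: "Participants will be admitted into the clinical site prior to study drug administration". The next sentence places dosing on that same day, Day 1, and the study schematic has no Day -1 column.

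**Dose changes.** Protocol 7.4: "No dose modifications are permitted during the conduct of the study or for 10 days prior to Day 1". This governs the dose and sets no clock time.

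**What is measured.** Protocol 9.5 defines Ctrough as "Trough observed plasma (predose) concentration" and C24 as "Observed plasma concentration at 24 hours postdose". AUC(TAU) is the area over one dosing interval. SAP 7.7.2 summarises the predose value as C0.

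**The concern.** Steady-state pharmacokinetics is the only objective. Protocol 5.4 rests the single-dose design on participants already being at steady state on once-daily dosing. C0, C24, AUC(TAU) and CLT/F will therefore be read as values from one regular 24 h interval.

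The text asks only that home doses keep a constant clock time, and nothing visible links that time to 9:00 am on Day 1. Someone who always doses at 9 pm follows every instruction and still has one short interval, immediately before sampling. The residue of the last evening dose then raises the predose level and lifts the whole Day 1 profile a little. If most participants dosed in the evening, the shift would run in one direction and would not average out.

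**Working it through.** **1. The plan's own precision.** Half-width = t(0.975, 7) × SD/√8 × √(χ²(0.80, 7)/7) = 2.3646 × SD × 0.3536 × √(9.803/7) = 0.9894 × SD. With SDs of 1.13, 9.03 and 138.1 this gives 1.118, 8.934 and 136.63. These match the stated 1.12, 8.93 and 136.63 (Protocol 10.1, SAP 5).

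**2. The gap.** From 9 pm on Day -1 to 9:00 am on Day 1 is 12 h instead of 24 h. That evening means 9 pm is an assumption; 6 pm to 11 pm gives 15 to 10 h.

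**3. Inputs (Protocol 3.2.4, healthy subjects, 0.5 mg).** Steady-state Cmax 4.2 and trough 0.3 ng/mL; about 2-fold accumulation; bi-exponential decline with terminal half-life 128-149 h; peak between 0.5 and 1.5 h.

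**4. Model.** C(t) = A·e^(-at) + B·e^(-bt) - (A+B)·e^(-kt), with b = ln 2/half-life, superposed over once-daily doses. It was solved for Cmax 4.2, trough 0.3 and accumulation 2.00, with an assumed single-dose peak at 0.5 h. Half-lives of 128, 138 and 149 h, each with steady state taken after 14 or 60 doses, give six exact fits. The reference is 60 earlier doses at 24 h spacing.

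**5. One case by hand (138 h, 60 doses).** A = 10.99, a = 1.17, B = 0.0385, b = 0.00502, k = 3.17. Regular dosing gives AUC(TAU) = A/a + B/b - (A+B)/k = 9.39 + 7.66 - 3.48 = 13.57 ng*h/mL and C0 = 0.300 ng/mL. By 12 h only the slow phase is left, so with r = 2^(-24/138) = 0.886:

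- C0: 2^(12/138) - 1 = +6.2%.
- C24: r × 6.2% = +5.5%.
- AUC(TAU): 0.300 × 0.062 × (1 - 0.886)/0.00502 = +0.42 ng*h/mL, and 0.42/13.57 = +3.1%.
- CLT/F = 500,000/(60 × AUC): 614 falls to 596 mL/min, about -3%.

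**6. Range over the six exact fits, 12 h gap.**

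| Parameter | Shift |
|---|---|
| C0 | +5.7 to +6.7% |
| C24 | +5.1 to +5.9% |
| AUC(TAU) | +2.9 to +3.7% (0.39 to 0.54 ng*h/mL) |
| CLT/F | -2.8 to -3.6% (17 to 20 mL/min) |
| Cmax | +0.4 to +0.6% |

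For evening times from 6 pm to 11 pm the AUC(TAU) shift is +2.1 to +4.3%.

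**7. Sensitivity to the peak time.** These narrow ranges rest on the 0.5 h peak. Peaks at 0.75, 1.0 and 1.5 h cannot reach 2-fold accumulation (1.79-1.84, 1.64-1.68 and 1.45-1.47), so those fits are not exact. They give AUC(TAU) +2.0 to +3.3%. C0 is +5.7 to +6.9% at 0.75-1.0 h and +12 to +15% at 1.5 h, where the fast phase has not finished by 12 h. The last figure depends on how the misfit is spread over the targets.

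**8. Effect on the study mean.** The mean shifts by the affected fraction times the individual shift. With 1 of 8 affected, C0 moves by about 6%/8 = 0.8% and AUC(TAU) by at most 0.54/8 = 0.07 ng*h/mL. With all 8 affected, AUC(TAU) moves by about 0.5 ng*h/mL, against a planned half-width of 8.93. The two sources differ (healthy-subject model, HBV-patient SDs), so this shows order of magnitude only.

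**9. What the fix leaves.** Home doses at 9:00 am ± 1 h and the Day 1 ± 30 minutes give gaps of 22.5 to 25.5 h: at most 2^(1.5/128) - 1 = 0.8% in C0 and 0.5% in AUC(TAU). An evening taker who changes over and then takes 10 morning doses keeps 6.2% × 2^(-240/138) = 1.9% in C0 and 3.1% × 0.30 = 0.9% in AUC(TAU). Over the fits and either direction of change this is about 1.7-1.9% and 0.9-1.1%. After 20 morning doses it is about 0.5-0.6% and 0.2-0.3%.

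**The case against.** The best reply is that the shift changes no conclusion. The study is descriptive, with about 8 participants and no comparator, test or acceptance limit. The one example time equals the Day 1 dose time, so the intent is clear, and nothing shows that any participant doses in the evening. All of this stands and is why the point is minor. It does not remove the gap: an intent shown by an example does not bind a participant or a site.

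A second reply is that unseen text may deal with irregular doses. The text of SAP 7.7.1 and 8.1.4, the CRF and the procedure manual is not available to this review, and no claim is made about it. Protocol 7.7.1 already asks for medications of the previous 4 weeks on the CRF, which may cover home Baraclude, though no clock time is mentioned. Recording or excluding would not prevent the short interval; the dosing instruction would.

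Two stronger readings are tempting, and the documents do not support them.

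- **A 36 h gap.** A reader might infer that the Day -1 evening dose is skipped around admission, which would move C0 by -5.4 to -6.3% and AUC(TAU) by -2.7 to -3.5%. The text points to admission on Day 1, so a compliant evening taker takes that dose at home. A 36 h gap needs a missed dose or an earlier admission, and neither is described.
- **A large bias in C0.** Putting the 24 h effective half-life into a single-exponential decline gives 2^(12/24) - 1 = +41%. That model implies a peak-to-trough ratio near 2, whereas the protocol reports 4.2/0.3 = 14 and a bi-exponential decline.

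**Conclusion.** The point holds as a minor one. The stated rule lets a compliant evening taker reach the Day 1 dose about 12 h after the previous dose, and the sample labelled trough is then not a 24 h trough. In that participant C0 is about 6% high (up to about 15% with a late absorption peak), C24 5-6% high, AUC(TAU) 2-4% high and CLT/F 2-4% low. C24 is correctly timed after the Day 1 dose but carries a similar shift, so it does not replace a regular trough.

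The size rests on healthy-subject values, an assumed 9 pm dose and an assumed early peak. The number of evening takers is unknown. The planned sample size and half-widths do not change, and nothing here suggests that the study would mislead about exposure.

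**What to change.** In Protocol 5.1 and SAP 2.1, replace the example with a requirement: take the home doses in the 10 days before Day 1, including the Day -1 dose, at about 9:00 am within a stated window. A window of ± 1 h is suggested here; it is an assumption, not a figure from the plan. Where screening falls earlier than Day -10, ask evening takers to change to mornings from that visit.

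Record the date and time of the last home dose if the CRF or procedure manual does not already ask for it. Flag participants outside the window in the PK listing, and keep them in the primary summary if they are otherwise evaluable.

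The cost is one sentence in each document, at most one date/time field and one listing flag. The burden falls on evening takers, who must change at least 10 days before Day 1; for anyone screened later than Day -10, Day 1 has to move back. A 10-day change still leaves about 2% in C0 and 1% in AUC(TAU), which is acceptable here.
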